
Outcomes
	
Primary outcome: All-cause hospitalization or death collected primarily by data provided by patients via the Patient and Call Center Portals, and review of electronic health records (I). Administrative and claims data will be reviewed to evaluate the completeness of ascertainment of the primary outcome. Trial data and National Death Index (NDI) will contribute to primary analyses of primary and secondary outcomes. Trial data, NDI, and Medicare data will contribute to secondary analyses of primary and secondary outcomes.
 
Secondary outcomes:
 
 • All-cause individual events: hospitalization, emergency department visit, urgent care visit, death (source: Participant Portal, Investigator Portal/EHR, Medicare claims data in a subset, NDI) • Patient-reported outcomes (source: Reference Table: PRO Common Measures, 3.1, Oct 25, 2014) PROMIS measures using the NIH-PROMIS instruments (source: Call Center or Participant Portal): 
 1. Physical function (Domain: Physical function (alternate), Item code: GLOBAL 06, Item bank: PROMIS Global) 2. Problems with sleep (Domain: Sleep disturbance, Item code: SLEEP20, Item bank: PROMIS Sleep Disturbance) 3. Fatigue (Domain: Fatigue, Item code: 2876R1, Item bank: PROMIS Peds - Fatigue) 4. Anxiety (Domain: Anxiety, Item code: EDANX53, Item bank: PROMIS Emotional Distress-Anxiety) 5. Depression (Domain: Depression, Item code: PEDGLOBAL2, Item bank: PROMIS Peds - Global) • Adverse events: patient report for hearing decrement, diarrhea, nausea, suicidal ideation, other (source: self-report via Call Center or Participant Portal); microbiology cultures in which macrolide-resistant organisms were identified in sputum (sole: EHR) • Medication adherence (source: self-report via Call Center or Participant Portal; Medicare claims data in a subset) • Crossover to alternate study medication (source: self-report via Call Center or Participant Portal, query of clinic staff; Medicare claims data in a subset) • Treatment discontinuation (source: self-report via Call Center or Participant Portal; query of clinic staff; Medicare claims data in a subset) • Out-of-pocket costs for roflumilast or azithromycin (source: self-report via Call Center or Participant Portal) • Weight (source: self-report via Call Center or Participant Portal)

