Site Coordinators will be asked to assist in locating patients who are lost to follow-up and in ascertaining or verifying hospitalizations and death. Site Coordinators will also submit data on patient outcomes, such as adverse events, all-cause hospitalization, changes to study medications, medical diagnoses, or other relevant information, and microbiology cultures in which macrolide-resistant organisms were identified in sputum from the EHR via ad hoc and end-of-study reports on the Investigator Portal ([Table 3](#)). We will ascertain vital status on all patients via the NDI after follow-up is completed.

In addition, we will work with the FDA Sentinel Operations Center (SOC) to obtain Medicare data regarding the claims for study medications and healthcare utilization for patients enrolled in Medicare.

Protocol Version 4.0

Data item	Sources (and estimated time for patients)	Baseline (BL)	1 week	3 and 6 mos after randomization, then every 6 mos until primary outcome is recorded or 36 months after start of enrollment, whichever occurs first.	End of study
Informed consent	Investigator Portal	X			
Demographics	Investigator Portal (3 min)	X			
Smoking status	Investigator Portal	X			
	Participant Portal/Call Center (2 min)			X	
PROMIS questionnaires (physical function, sleep disturbance, fatigue, anxiety, depression)	Investigator Portal	X			
	Participant Portal/Call Center (2 min)		X (if not done at BL)	X	
Height, weight	Investigator Portal	X			
	Participant Portal/Call Center (2 min)			X	
Study treatment (adherence, treatment discontinuation, cross-over to alternate medication)	Investigator Portal	X			
	Participant Portal/Call Center (3 min)		X	X (and ad hoc)	
	Claims databases				X
Out-of-pocket costs	Participant Portal/Call Center (2 min)		X	X	
Healthcare utilization	Investigator Portal	X			X
	Participant Portal/Call Center (5 min)		X	X (and ad hoc)	
	Claims databases				X
	National Death Index				X
Adverse events (hearing decrement, diarrhea, nausea, suicidal ideation)	Participant Portal/Call Center (3 min)		X	X (and ad hoc)	
	Claims databases				X
Adverse event (microbiology cultures of macrolide resistant organisms in sputum)	Investigator Portal				X

Protocol Version 4.0

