2.3. Linkage with Medicare Data

Linkage of the RELIANCE trial to Medicare claims data for a secondary analysis will provide additional information regarding use of the study drugs, the primary outcomes and select secondary outcomes that can be assessed with Medicare data, and will also provide an opportunity to test distributed regression methods with vertically partitioned data. In collaboration with the FDA Office of Medical Policy, the Sentinel SOC will work with the Department of Population Health Sciences (DPHS) at the Duke University to link patients enrolled in the RELIANCE trial to Medicare data. The SOC is located at Harvard Pilgrim Health Care Institute and collaborates with the DPHS on specific Medicare linkage activities. The general process for linkage is described below. A more comprehensive Appendix detailing measures to minimize breaches and protect identifiable data, plans for final disposition of identifiers, and movement of direct identifiers will be submitted to the IRB for review prior to the initiation of data transfer.

The general process for Medicare data linkage will be as follows: The DCC will provide SOC a file with direct patient identifiers (i.e., SSN ± Health Insurance Claims Number (HIC/MBI), date of birth, sex) required for Medicare data linkage. SOC will process these data according to CMS requirements, and will submit this information to CMS via encrypted physical media, or other methods required by CMS (or their designee). CMS then will link trial participants to Medicare enrollment file, create a crosswalk file, and extract the requested Medicare data. CMS will then send the extracted Medicare data files to SOC and the DCC. Finally, the DCC will provide SOC with data from the RELIANCE trial required for the distributed regression methods evaluation. We anticipate using enrollment, inpatient claims, and annual Part D medication dispensing data for RELIANCE trial participants enrolled in Medicare to assess the completeness of ascertainment of the primary outcomes (death or all-cause hospitalization) and evaluate adherence to the assigned treatment. In addition, secondary analyses will evaluate other aspects of healthcare utilization, e.g., urgent care and ED visits.

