There is considerable debate about the optimal approach to analysis of non-inferiority trials, as randomized or per protocol. The major concern about as randomized analyses for non-inferiority hypotheses is that if a significant number of patients do not adhere to their assigned treatment, the test treatments may falsely appear to have similar effects thereby introducing a bias favoring a conclusion of non-inferiority. Per protocol analyses, which limits the analyses to the subgroup of patients who adhere to their assigned treatment, are recommended for testing non-inferiority hypotheses primarily to avoid this potential bias. However, per protocol analyses of non-inferiority trials have all the same flaws as they do in superiority trials.⁵³ For example, if patients discontinue study assigned treatments because of side effects, the potential decreased effectiveness of the treatment is correctly attributed to the assigned treatment in an as randomized analysis but would not be in a per protocol analysis. The preferred approach is to maintain as randomized ITT as the primary analysis and to institute performance measures that ensure the integrity of the trial and provide essential information for interpretation of the results.⁵⁴ Per protocol analysis will be a key secondary analysis and will be compared with the as randomized analysis. Data on protocol performance such as treatment adherence, losses to follow-up and missing data will be used to help understand and interpret differences, if any, in the results of the two methods.

The primary outcome is the time to first all-cause hospitalization or death. Individuals without an event will be censored at the date of last contact. A Cox proportional hazards model will be used to assess whether azithromycin is non-inferior to roflumilast. Non-inferiority will be achieved if the upper boundary of the confidence interval for the hazard ratio (azithromycin/roflumilast) is

Protocol Version 4.0

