3.4. Missing Data

As noted in the IOM Guidelines, prevention is the most important method for handling missing data.⁵⁷ The recommended strategies include careful consideration of potential barriers to data collection during the design phase of the trial, including patient and outcome selection. For example, an advantage to our choice of the primary outcome, all-cause hospitalization or death, is that it can be measured and confirmed from numerous sources. The primary source of outcome data will be from patients. In addition, we have planned a number of strategies to limit missing data during the execution of the trial. As noted above, we will rely on several sources of data to ascertain the primary outcome measures of all-cause hospitalization and mortality including patient reports supplemented by administrative data from CMS and the NDI and follow-up data collected by Site Coordinators. For patient-reported outcomes, we will employ several strategies to prevent missing data, including collection of multiple contacts, verification of phone numbers, email addresses, and secondary contacts including relatives or neighbors, and healthcare providers. Patients will be reminded about outstanding questionnaires via emails and texts backed-up with phone calls. Clinical centers will review the EHR periodically and administrative sources will also be used to identify unreported events. If we are unable to contact the patient via those measures, Site Coordinators will be asked to “find” those patients and collect the missing data. We will also employ real-time data performance reporting so that we can monitor trends in missing data to identify problems and develop interventions. Data on treatment adherence and outcomes will be extracted from CMS administrative database on the subset of patients enrolled in Medicare via a collaboration with the FDA Sentinel Program. We will also use the NDI to identify unreported

Protocol Version 4.0

deaths in the entire study group.

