All patients will be accounted for in analyses. For the primary outcome (hospitalization or death), a Cox proportional hazards model will be used. Individuals who are lost to follow-up are censored at the time of the last known contact and so all individuals with follow-up may be included in the analyses. Data collected up until the time of withdrawal will be retained from those participants who do not continue on in the study. Issues with missing data arise if the censoring mechanism is related to the outcome of interest. The range of potential influence will be established by imputing the 'best' and 'worst' case scenarios. Analytic methods will be used to assess the censoring patterns. Based upon these findings, sensitivity analyses using multiple imputation, inverse probability weighting, or a pattern mixture approach will be used.^{46,47} For non-time to event outcomes, the primary analysis will be based upon mixed effects models (for replicate measurements over time) or multiple imputation (for single measurements), both of which are robust to data that is missing at random. 'Best' and 'worst' case analyses similar to those used for time-to-event outcomes will also be used to gauge the potential effect of missing data.

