Reasons for missing data will be assessed for all data sources. For data collected from clinical centers, the reason for missing data will be collected directly from the clinic, e.g., data not assessed, patient refused or no follow-up for patient at the clinical center. The Call Center will record attempts to remind and collect data for patient-reported outcomes. These will include patient refusal, inability to contact patient, or death. In comparative effectiveness trials where the hypothesis is non-inferiority, treatment cross-overs, treatment cessation, lack of adherence, and loss to follow-up tend to support the inference of non-inferiority between treatment groups. To some extent, these deviations from protocol are the rationale for conducting a "real-world" pragmatic trial. Interpretation of these factors can be assisted by comparison of as randomized and per protocol analyses as well as sensitivity analyses of specified subgroups. However, failure to ascertain the primary outcome, particularly if there is differential data loss between treatment groups is a serious threat to the validity of the trial and there is no analytic technique that can completely overcome this. In this trial, we are proposing to use multiple data streams including EHRs, directly from patients and providers, and from CMS administrative datasets and NDI administrative datasets for the primary outcome, we should be able to have virtually complete ascertainment of hospitalizations and deaths for this largely Medicare population.

Protocol Version 4.0

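### Lost participants are censored at last contact, but NDI deaths after that contact still count, so time at risk in the primary analysis depends on the outcome; the role of CMS data also needs reconciling

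*Protocol*

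**What the plan says.** **Censoring.** Section 3.2 (Analysis Plan) defines the primary outcome as time to first all-cause hospitalisation or death and states: "Individuals without an event will be censored at the date of last contact". Section 3.4 (Missing Data) says the same of loss: "Individuals who are lost to follow-up are censored at the time of the last known contact".

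**NDI.** The Outcomes row of the PICOTS table says: "Trial data and National Death Index (NDI) will contribute to primary analyses of primary and secondary outcomes". Section 2.2 (Data Collection) says: "We will ascertain vital status on all patients via the NDI after follow-up is completed". Section 3.4 adds "We will also use the NDI to identify unreported" deaths, and applies this to the whole trial population. No section limits these deaths to those before last contact, and none carries survivors forward to an NDI date.

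**CMS (Medicare).** The PICOTS table adds Medicare data only for secondary analyses. Section 2.2 uses Medicare and NDI data to check how complete outcome ascertainment is. Section 2.3 describes "Linkage of the RELIANCE trial to Medicare claims data for a secondary analysis", together with completeness checks. Section 3.4, however, lists as sources for the primary outcome "patient reports supplemented by administrative data from CMS and the NDI and follow-up data collected by Site Coordinators", and later says that with data "from CMS administrative datasets and NDI administrative datasets for the primary outcome, we should be able to have virtually complete ascertainment" of hospitalisations and deaths.

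**The concern.** A Cox analysis needs the end of a person's time at risk to be set without reference to whether an event follows. Here it is not. Take two participants who both stop responding at month 9 without an event. The NDI search at study end covers both. If the first died at month 20, that person is at risk for 20 months and contributes an event. If the second is alive, the time stops at month 9. The months that the survivor lived after loss are dropped, although the same search shows the person alive.

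Each arm's apparent event rate is therefore inflated in proportion to its loss. If the arms lose participants at different rates, the inflation does not cancel in the hazard ratio. Against a margin of 1.2, greater loss on roflumilast pushes towards a false non-inferiority claim, and greater loss on azithromycin costs power. Section 3.4 itself treats differential loss of primary-outcome data as a serious threat to validity, so the primary rule should not turn such loss into bias.

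The CMS inconsistency has the same root. If claims-only hospitalisations count, they too would enter after last contact for some participants without matching time for the others. The primary event count also depends on which section is followed.

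**Working it through.** **Inputs from the protocol.** N = 3,200 (1:1), 30% with an event at one year, 5% loss per year, 30 months' accrual plus 6 months, margin 1.2, one-sided 0.025 (Section 3.1); 1,368 expected events (Section 3.5). One-year mortality after a COPD admission is given as 7% to 50% (Section 1.1).

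**Assumptions (not in the protocol).** Loss by arm; death hazard μ after loss; exponential times; uniform accrual.

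**1. The plan's own figures.** Event hazard λ = −ln(0.70) = 0.3567 per year; loss hazard η = −ln(0.95) = 0.0513; sum 0.4080. Follow-up C is uniform on 0.5 to 3 years, so the mean of 1 − exp(−0.4080·C) is 0.4888.
- Events = 3,200 × (0.3567/0.4080) × 0.4888 ≈ 1,367.5 (stated 1,368).
- Power = Φ(√1368 × ln 1.2 / 2 − 1.96) = Φ(1.41) = 92.1% (stated 92%).

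**2. Participants lost event-free.** 3,200 × (0.0513/0.4080) × 0.4888 ≈ 197.

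**3. NDI deaths after last contact.** 3,200 × mean over C of ∫₀^C η·exp(−0.4080u)·[1 − exp(−μ(C−u))] du:

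| μ per year | late deaths |
|---|---|
| 0.07 | 15 |
| 0.12 | 24 |
| 0.15 | 30 |
| 0.20 | 38 |
| 0.30 | 53 |
| 0.50 | 78 |

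At 5% loss the apparent hazard in an arm rises from 0.3567 to 0.3595 (μ = 0.07), 0.3623 (μ = 0.15) or 0.3721 (μ = 0.50), that is, by about 1% to 4%.

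**4. Effect on the hazard ratio (azithromycin/roflumilast), by simulation at true HR 1.20 and μ = 0.12.** The error column is Φ(−1.96 + ln(HR with common date / HR as written)/SE), with SE = 2/√1368 = 0.0541.

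| Loss per year, roflumilast vs azithromycin | Common end date | Rule as written | One-sided error |
|---|---|---|---|
| 6% vs 4% | 1.196 | 1.189 | about 3% |
| 8% vs 3% | 1.201 | 1.185 | about 4% |
| 15% vs 5% | 1.199 | 1.165 | about 8% |

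Example: ln(1.199/1.165)/0.0541 = 0.53, and Φ(−1.96 + 0.53) ≈ 0.08.

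With equal 5% loss the HR is 1.00 at the null. At true HR 1.20 it is 1.197 (μ = 0.15) or 1.193 (μ = 0.30), with post-loss mortality taken as the same in both arms.

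Reversed direction, with azithromycin 10%, roflumilast 5% and μ = 0.30: a true HR of 1.20 is estimated as 1.226. A true HR of 1 is estimated as 1.031, with power about 81% instead of 91%.

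**5. Candidate end dates.**
- Last contact for both events and non-events: 1.199 at true HR 1.20, so unbiased.
- First missed scheduled contact, on the protocol's 3-, 6- and then 6-monthly schedule with hospitalisations after last contact unseen: 1.216 at roflumilast 8% vs azithromycin 3%, and about 1.18 with the rates reversed. The bias changes sign.
- Lost survivors kept at risk to study end: HR 1.028 at the null (roflumilast 10%, azithromycin 5%, μ = 0.15), because their later hospitalisations are unseen.

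**The case against.** Four points can be made for the plan.

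**The protocol never says how an NDI death after last contact enters the time variable.** Section 2.2 calls NDI a completeness check, and date derivation is commonly left to an SAP. This stands in part: an SAP could cure the problem. But the protocol states both the censoring date and the entry of NDI deaths into the primary analysis, and an SAP that applied both as written would inherit the defect.

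**Unequal loss has no basis in the documents.** This stands. Section 3.1 plans 5% per year overall. A reader might infer from the open-label design and differing tolerability that roflumilast will lose more, so that a false non-inferiority claim is likely. The protocol does not support that. Section 1.1 puts excess discontinuation at 5 to 6% for either drug. Stopping treatment is not loss to follow-up here, because participants are followed whatever their adherence and there are no study visits. A 15% annual loss is about 39% over three years (1 − 0.85³), far from the plan.

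**Section 3.4 already plans sensitivity analyses** (best and worst case, multiple imputation, inverse probability weighting, pattern mixture). They may expose the effect but leave the primary rule unchanged.

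**On CMS,** a reader might go further and infer that leaving claims out of the primary analysis brings power below 92%. The documents do not support this either. They give no capture rate for trial sources, and the 92% rests on an assumed 30% one-year event rate that is not tied to any data source.

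**Conclusion.** The point holds as a defect in a stated rule, of modest and conditional size. Read together, the sections make time at risk after loss depend on whether the person later dies.

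Under the planned 5% loss in both arms the HR is essentially unbiased. At 6% vs 4% the shift is under 0.01. At 8% vs 3% to 15% vs 5% it is about 0.015 to 0.035, taking one-sided error from 2.5% to roughly 4% to 8% if roflumilast is the arm losing more; the shift runs the other way if azithromycin is. These figures rest on assumed loss by arm and an assumed death hazard of 0.12 per year; higher mortality after loss enlarges them. Nothing in the protocol shows which direction, if either, will occur.

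The CMS point is a contradiction in the text: the PICOTS table and Sections 2.2 and 2.3 against Section 3.4. No effect on power can be derived from it. The protocol should be amended, because the correction is cheap and best settled before unblinded results are seen.

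**What to change.** In Sections 3.2 and 3.4, define one end-of-follow-up date for events and non-events: the last contact at which hospitalisation and vital status were both ascertained from trial sources (patient, proxy, site or EHR), or study close.

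For participants lost to follow-up, do not count NDI-only deaths after that date in the primary composite. Use them for the all-cause death outcome, with everyone followed to a common NDI date, and in a sensitivity analysis of the composite. Amend the PICOTS sentence on NDI to match.

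Do not use the first missed scheduled contact as the end date, and do not simply keep lost survivors at risk to study end. Hospitalisations after last contact are unseen in both cases, and both gave biased estimates above.

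Separately, state once whether CMS-found events count in the primary analysis. If they do not, as the PICOTS table and Section 2.3 indicate, remove CMS from Section 3.4 as a primary-outcome source and as a basis for its claim of near-complete ascertainment. If they do, amend the PICOTS table and Sections 2.2 and 2.3, and apply the same end-date principle to claims.

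The cost is wording only, with no new data. About 15 to 40 late deaths (assumed mortality 7% to 20% per year) leave the primary analysis, against 1,368 expected events.

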1.5. Warnings and Precautions

The list below is reproduced from the FDA's highlights of prescribing information. Additional details are presented elsewhere in the prescribing information document.

For azithromycin (version 4/2019)

- Serious (including fatal) allergic and skin reactions: Discontinue azithromycin if reaction occurs.
- Hepatotoxicity: Severe, and sometimes fatal, hepatotoxicity has been reported. Discontinue azithromycin immediately if signs and symptoms of hepatitis occur.
- Prolongation of QT interval and cases of torsades de pointes have been reported. This risk, which can be fatal, should be considered in patients with certain cardiovascular disorders including known QT prolongation or history of torsades de pointes, those with proarrhythmic conditions, and with currently taking other drugs that prolong the QT interval.
- Clostridium difficile-associated diarrhea: Evaluate patients if diarrhea occurs.
- Azithromycin may exacerbate muscle weakness in persons with myasthenia gravis.

For roflumilast (version 1/2018)

- Acute bronchospasm: do not use for the relief of acute bronchospasm.
- Psychiatric events including suicidality: advise patients, their caregivers, and families to be alert for the emergence or worsening of insomnia, anxiety, depression, suicidal thoughts or other mood changes, and if such changes occur to contact their healthcare provider. Carefully weigh the risks and benefits of treatment with roflumilast in patients with a history of depression and/or suicidal thoughts or behavior.
- Weight loss: monitor weight regularly. If unexplained or clinically significant weight loss occurs, evaluate weight loss and consider discontinuation of roflumilast.
- Drug interactions: use with strong cytochrome P450 enzyme inducers (e.g., rifampicin, phenobarbital, carbamazepine, phenytoin) is not recommended.

Protocol Version 4.0

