less than 1.2, the non-inferiority margin. The level of the confidence interval will be adjusted from 95% to account for type I error spending during interim efficacy analyses and will match the type I error used in the final analysis. If we achieve non-inferiority, then an additional test for superiority will be performed. The primary analysis will adjust for the stratification variables smoking status (current vs former) through the inclusion of a fixed effect and clinic with a random effect, respectively. A key secondary hypothesis is that the treatment effect will differ for current and former smokers. A test of interaction will be used to assess the heterogeneity of treatment effects (HTE) based upon smoking status (current vs former). Secondary analyses will be performed both adjusting for and investigating the HTE for key baseline characteristics including but not limited to 3 pre-specified comparisons: a history of asthma (yes vs no), gender (male vs female) and BMI (obese vs not obese).

Analysis of secondary outcomes by treatment group will employ negative binomial, logistic, linear and Cox proportional hazards models for event rates, binary outcomes, continuous outcomes, and time to event outcomes, respectively. Mixed effects models will be used to model outcomes with repeated measurements over time. Both unadjusted and adjusting models including the stratification variables (clinic and smoking status) as well as clinically important risk factors (e.g. history of asthma, gender, BMI, medication use) will be explored. Summary statistics, model estimates with confidence intervals and p-values will be used to present the findings. A large number of analyses, including HTEs, are planned and caution is necessary in interpreting the results especially since it is generally not possible to pre-specify all potential analyses. The number of secondary analyses explored will be clearly specified and the expected number of false positives will be calculated and included in the presentation of our results. Several methods of adjusting p-values for multiple comparisons exist; however, no clear consensus as to the most appropriate method is available. As recommended by Wang and Lagados, reporting will focus on point estimates and confidence intervals as well as p-values and reports will be considered hypothesis generating.⁴⁴

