Macrolides (including azithromycin) are known to cause ventricular arrhythmias that could be fatal, but the incidence for long-term azithromycin use to prevent COPD exacerbations is unknown. On the basis of results published in an observational study using claims data, the FDA re-iterated the importance of carefully reviewing patient-level risk factors (history of prolonged QT interval, comorbid condition, or arrhythmogenic potential of other co-therapies) when using azithromycin.^{60,61} The incidence of arrhythmias with macrolides in the absence of additional risk factors is estimated to be very low, perhaps <1 in 100,000 individuals.

In a Cochrane review of placebo-controlled efficacy trials of roflumilast, premature treatment discontinuation due to adverse effects was more common with roflumilast than with placebo (15 vs. 9%, $p<0.05$; 9,511 patients).²⁸ The most common adverse effects that were also more common in the roflumilast group included diarrhea (10 vs. 3%, $p<0.05$), nausea (5 vs. 1%, $p<0.05$); weight loss (8 vs. 2%, $p<0.05$), psychiatric disorders (7 vs. 4%, $p<0.05$; includes anxiety, depression); and sleep disturbances/insomnia (3 vs. 1%, $p<0.05$). Mortality was low in the trials of roflumilast, with no significant difference between groups (roflumilast vs. placebo: 2 vs. 2%). A similar increase in adverse effect-associated treatment discontinuation was noted in comparative trials of up to 12 months in the REACT, RESPOND² and M2-124 and M2-12533 studies (12 vs. 8% placebo). The most common adverse effects that were also more common in the roflumilast group included diarrhea (17 vs. 6% placebo), weight loss (9 vs. 3% placebo). The OPTIMIZE study found that premature treatment discontinuation can be reduced by initiating treatment with a 4-week course of 250 mcg/day of roflumilast before dose-escalation to 500 mcg/day.

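### The pre-specified BMI effect-modifier comparison is an obesity split, which gives up information that planned baseline height and weight would supply; using continuous BMI is an optional, cheap improvement

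*Protocol*

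**What the plan says.** Section 3.2 (Analysis Plan) says that secondary analyses will adjust for key baseline characteristics and examine heterogeneity by them, "including but not limited to 3 pre-specified comparisons". The three are history of asthma, gender and BMI, the last two written as "gender (male vs female) and BMI (obese vs not obese". No BMI value defining obesity is given.

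The next paragraph of Section 3.2 lists BMI among possible adjustment covariates: "clinically important risk factors (e.g. history of asthma, gender, BMI, medication use) will be explored". It gives no functional form for BMI there. The same paragraph urges caution about the number of analyses, promises a count of expected false positives, and ends by saying that "reports will be considered hypothesis generating".

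Table 3 (Section 2.2) has a row "Height, weight" marked at baseline through the Investigator Portal and again at follow-up. Weight is a secondary outcome under secondary aim 2 (Section 1.2).

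On roflumilast and weight, Section 1.5 reproduces the label warning "Weight loss: monitor weight regularly". Section 4.3 reports weight loss in earlier trials as 8% vs. 2% on placebo in a review, and 9% vs. 3% in later trials. Neither section links weight loss to BMI at baseline.

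**The concern.** Asthma history and gender are entered as categories. BMI is the only one of the three that is a measurement cut in two. The protocol states this form outright, so it is not merely a detail left open for a statistical analysis plan.

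A two-way cut has two consequences. First, if the treatment effect changes gradually with BMI, the cut discards part of the information and the interaction test loses power. Second, underweight, normal and overweight patients all fall in the not-obese group, so a difference that exists only at low BMI is averaged with many patients who do not have it. What is at stake is how informative one secondary analysis can be.

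**Working it through.** **The design figures reproduce.** Inputs from Sections 3.1 and 3.5: 3,200 patients, 1:1 allocation, 30% with an event at one year, 5% loss per year, 30 months of accrual plus 6 months of follow-up, margin 1.2, one-sided 0.025, 1,368 expected events.
- Exponential event times with uniform accrual give an event probability of 0.4273, and 3,200 × 0.4273 = 1,367 events (stated: 1,368).
- Power = Φ(½ × √1,368 × ln 1.2 − 1.960) = Φ(3.372 − 1.960) = 0.921 (stated: 92%).

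The protocol states no figure for the BMI analysis.

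**Information kept by the split.** Assumptions: normal BMI, interaction linear in log hazard ratio, and a share p obese, which the protocol does not give. With c the standard normal value exceeded with probability p, the share kept is r = φ(c)² / [p(1 − p)]. For p = 0.30, c = 0.524 and φ(c) = 0.348, so r = 0.348² / 0.21 = 0.576.

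**Power after the split.** An interaction with 80% power on one continuous term (two-sided 5%) has a standardised effect of 1.960 + 0.842 = 2.802. After the split, power = Φ(2.802 × √r − 1.960). For 90% power, replace 2.802 by 3.242.

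| Assumed obese | Kept | Lost | Power, was 80% | Power, was 90% |
|---|---|---|---|---|
| 20% | 0.490 | 51% | 50% | 62% |
| 25% | 0.539 | 46% | 54% | 66% |
| 30% | 0.576 | 42% | 57% | 69% |
| 35% | 0.603 | 40% | 59% | 71% |
| 40% | 0.622 | 38% | 60% | 73% |
| 50% | 0.637 | 36% | 61% | 73% |

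Under these assumptions the loss is smallest at a median cut: 1 − 2/π = 36%.

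**Detectable interaction with 1,368 events, 80% power.**
- Split: standard error √[4 / (1,368 p(1 − p))] = 0.118 at 30% obese and 0.108 at 50%. The detectable ratio of hazard ratios is exp(2.802 × 0.118) = 1.39 and exp(2.802 × 0.108) = 1.35.
- Continuous: standard error √(4 / 1,368) = 0.0541 per SD, so exp(2.802 × 0.0541) = 1.16 per SD.

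**Dilution of a low-BMI effect (illustration only).** Assume 10% of patients have low BMI and a hazard ratio of 1.5, all others have 1, and events are spread evenly.
- Not-obese hazard ratio: exp(ln 1.5 × 0.10/0.70) = 1.06 at 30% obese; exp(ln 1.5 × 0.10/0.60) = 1.07 at 40%.
- Split test: 0.0579/0.118 = 0.49 and 0.0676/0.110 = 0.61 standard errors, or about 8% and 9% power.
- Linear continuous term: slope ln 1.5 × φ(1.282) = 0.4055 × 0.1755 = 0.0712 per SD; 0.0712/0.0541 = 1.32 standard errors, about 26% power.
- Contrast of the low 10% with the rest: standard error √[4 / (1,368 × 0.10 × 0.90)] = 0.180; 0.4055/0.180 = 2.25, about 61% power.

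**The case against.** **The list is open and the analysis is exploratory.** This stands. Section 3.2 does not rule out a continuous-BMI interaction, and an analysis plan that is not at hand may add one. A reader might infer that heterogeneity by BMI will be tested only by the split; the text does not say so. It says only that the split is the pre-specified form. A continuous analysis added later would lack that status, which is what remains of the point.

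**The low-BMI argument is not the protocol's.** This also stands. A reader might infer from the weight-loss warning that low-BMI patients are the group of concern. Sections 1.5 and 4.3 report weight loss as an adverse effect and say nothing about baseline BMI. Weight is also followed as its own outcome, which the split leaves untouched.

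**A low-BMI effect would not necessarily be missed.** Correct: detection depends on its size. Nor would a low-BMI subgroup estimate be precise. With 5% to 10% of 1,368 events (68 to 137), the 95% interval extends by a factor of exp(1.96 × √(4/events)), about 1.6 to 1.4, on either side.

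**A spline can use up the gain.** At the same noncentrality of 2.802² = 7.85, a joint test has about 71% power on 2 degrees of freedom and 64% on 3. The recommended test is therefore the one-degree-of-freedom term, with the spline descriptive.

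**Two further limits.** Table 3 shows planned collection; it does not show that BMI will be complete for every patient. And since no form is given for BMI as an adjustment covariate, there is nothing to correct there.

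**Conclusion.** The point holds as an optional improvement. The pre-specified BMI comparison is a two-way split of a measurement the trial plans to collect. With normal BMI and a linear interaction, it loses 36% to 46% of the information on that interaction for 25% to 50% obese, and 51% at 20%; 80% power on a single continuous term becomes about 54% to 61%. The obese share, the normality and the linearity are all assumptions. If the effect really steps at the obesity threshold, the split is the right model and the loss is nil; the protocol gives no reason to expect a step. Dilution of a low-BMI effect is real arithmetic applied to a hypothetical effect.

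A reader might take a loss of about 40% as a loss of trial events or of primary power. It is neither: the non-inferiority test, the 3,200 patients and the 1,368 events are unaffected, and the key heterogeneity hypothesis concerns smoking.

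**What to change.** In Section 3.2, replace the pre-specified BMI comparison by a one-degree-of-freedom test of treatment by continuous baseline BMI. Add a restricted cubic spline as a supporting, descriptive look at curvature. This matters because a linear term alone is weak against an effect confined to one end of the range. Report the azithromycin/roflumilast hazard ratio with its confidence interval at BMI values stated in advance, including the low end. Keep the obese/not-obese split as a display row, with its cut-off stated.

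The cost is a sentence or two in the protocol and one extra figure, with no new data. Estimates at the extremes of BMI will be imprecise and should be presented as such.
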